6. * Since a separate protocol document is not uploaded, describe the proposed research using language understandable to those IRB committee members whose expertise is not scientific. The description must include:

1. A statement explaining the study design

2. A detailed description of all the procedures that will be followed to carry out the study, preferably in sequential order, and in sufficient detail that the study's methods could be replicated

3. A description of all research measures/tests/interventions that will be used (if applicable)

See the help text for additional guidance

1.

Randomized Controlled Trial.

The biostatistician on the study team ([name]) will generate random sequence in blocks of 4 using a computer.

All study participants will be assigned a unique identifier (4 digit code) generated by the study team based on order of enrollment and the type of attachment. The key that links code to the patient will be stored in the PI's office computer that has restricted access (only to study personnel). The key will be destroyed when the study is completed.

2.

Members of the study team including residents, [name] will have a meeting prior to start of the study to calibrate on the screening criteria to determine eligibility as well as obtaining signatures and maintaining the consent documents. The team will also have a virtual meeting over zoom at least once a month to update on study progress.

All members of the study team will inform [name] when a study participant is recruited to the study through a secure email. [name] will then communicate the randomly assigned attachment design to the treating orthodontist based on the sequence generated by [name]. The treating orthodontist will then put this information as an order to Align Technology for the fabrication of the attachment trays and clear aligners.

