During the scheduled appointment for the delivery of aligners, the patients will be instructed on how to properly place and remove aligners and their maintenance. Patients will be instructed to wear each aligner for a minimum of 22 hours a day for 7 days. Participants will verbally confirm compliance at each appointment. At the end of a series of 20-25 aligners, another intraoral scan will be taken and sent to Align Technologies to determine the final positions of the teeth. Comparison of initial and final positions (using Geomagic software) will be done to assess the efficacy of different types of attachments in lateral incisor extrusion.

Once the teeth are in desired positions, the treating orthodontist will remove the attachment (<6 months).

3.

Research related interventions include:

- a. random assignment of the specific type of attachment on lateral incisor;
- b. treating orthodontist placing the corresponding order in the prescription with Align Technology;
- c. delivery of attachments and aligners to the study participants
- d. Superimposition of final and initial positions of lateral incisors: Two superimpositions will be completed. The pretreatment model will be superimposed with the predicted final model to establish the predicted movement of the maxillary lateral incisors. The pretreatment model will be superimposed with the posttreatment model to establish the actual movement of the maxillary lateral incisor. The actual and predicted movement values will be calculated by the GeoMagic software. The amount of extrusion for the lateral incisors will be analyzed in increments of 0.1 mm.

Sample size: 80 maxillary lateral incisors with at least 20 teeth per study group. Randomization will occur at the level of individual lateral incisor tooth.

Study Duration: Patients will be evaluated only after the first series of aligners (20-25). Each set of aligners would be worn for a week and the study would span 20 - 25 weeks.

7. * The IRB only reviews research activities, so indicate which of the study activities are:

- **Being performed exclusively for research purposes (i.e. they would not otherwise be done apart from this study) VERSUS.**
- **Alterations of routine activities/procedures (e.g. the study is altering the timing, frequency, method, location, amount, etc.) VERSUS.**

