Costs to Participants

1. * Select all categories of costs that participants or their insurance companies will be responsible for:

- Participants will have no costs associated with this study
- Study related procedures that would be done under standard of care
- Study related procedures not associated with standard of care
- Administration of drugs / devices
- Study drugs or devices
- Other

ID: HM20021396

View: SF2 - Compensation

Compensation

1. * Describe any compensation that will be provided including:
 1. total monetary amount
 2. type (e.g., gift card, cash, check, merchandise, drawing, extra class credit)
 3. how it will be disbursed

Every lateral incisor that requires extrusion and qualifies for the study will be compensated with a \$50 gift card. The compensation will be distributed to study participants in person when they complete the second intraoral scan at the end of their initial series of clear aligners. Since there are two lateral incisors, a study participant's potential compensation can be \$100 if both their lateral incisors qualify for the study.

2. If compensation will be pro-rated, explain the payment schedule.
Compensation will not be pro-rated.

3. * Will Social Security Numbers be collected for compensation purposes only?

Yes
 No

ID: HM20021396

View: SF2 - Research Plan Complete

Research Complete

Protocol Progress:

- ? INITIAL SETUP
- ? BACKGROUND, RATIONALE & GOALS
- ? RESEARCH PLAN
- ? CONSENT PLAN
- ? RISKS, PRIVACY & CONFIDENTIALITY
- ? POPULATIONS WITH SPECIAL CONSIDERATIONS
- ? INSTITUTIONAL REQUIREMENTS
- ? DOCUMENTS

Click Continue below to go to the next section

ID: HM20021396

View: SF2 - Consent Process

Consent Process

1. * List all consent groups:

Group Types	Waivers	Roles	Roles - Other	Consent	Coercion	Decision	Re-Consent

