The study is a 4-arm randomized trial. Subjects will be screened for eligibility based on inclusion/ exclusion criteria. Once informed consent is obtained, the participants will be randomly assigned to one of the four attachment designs. The biostatistician on the study team ([name]) will generate random sequence using a computer. The randomization will be in block of 4 and the list will be provided to the study team.

All study participants will be assigned a unique identifier (4 digit code) generated by the study team based on order of enrollment and whether they received horizontal, incisally bevelled, gingivally bevelled or optimized attachments. This key that links code to the patient will be stored in the PI's office computer that has restricted access (only to study personnel). The key will be destroyed when the all participants complete their second scan (data collection is complete).

All data records used for analysis will have this assigned code without any identifying information. This will minimize the amount of recontacting needed for children who turn 18 during data analysis stage.

ID: HM20021396

View: SF2 - Data Retention

Data Retention

1. * **Select all of the ways that individually identifiable information obtained during pre-screening and/or screening will be handled for individuals who DO NOT qualify for the study:**
 - Immediately destroy the information and identifiers (no data collected)
 - Immediately destroy the identifiers connected with the data (anonymization)
 - Store until the end of study & then destroy
 - Use as "screening failure" data by members of the study team
 - Provide to others outside of the research team (with the participant's permission)
 - Request permission from participant to maintain and use the identifiable information
 - Other
 - N/A - study does not require screening procedures**
2. * **Will participants be able to withdraw their data (paper, electronic, or specimens) from the study (e.g. ask that it be destroyed or returned) if they no longer wish to participate? (FDA-regulated studies should select No - see help text)**
 - Yes
 - No**
3. * **What will happen to the research materials (e.g. data, specimens, documents, etc.) when the research has been completed?**
 - Stored indefinitely with identifiers removed
 - Stored indefinitely with identifiers attached

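### One fixed block size of 4 for four open arms makes the next design partly predictable to anyone who sees every prior assignment, even if the list is withheld

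*Combined protocol and SAP*

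**What the plan says.** - **Block size.** Study Procedures, Q6 (item 1) says that the biostatistician "will generate random sequence in blocks of 4 using a computer". Data Confidentiality and Storage, Q9 repeats it: "The study is a 4-arm randomized trial", and "The randomization will be in block of 4 and the list will be provided to the study team". No varying or concealed block size is mentioned.
- **Openness.** In Study Procedures, Q6 (item 2), a team member is told of each recruit and "will then communicate the randomly assigned attachment design to the treating orthodontist", who then orders it. For the Richmond practice, Non-VCU Site Details names the principal investigator as the person who relays the design. The Consent Process table lists the principal investigator among those who obtain consent.
- **Participant code.** It is "generated by the study team based on order of enrollment and the type of attachment".
- **Unit.** Study Procedures, Q6 (sample size) plans 80 teeth with at least 20 per group and says "Randomization will occur at the level of individual lateral incisor tooth". Compensation, Q1 provides for a double payment "if both their lateral incisors qualify for the study". Data Confidentiality and Storage, Q9 instead has each participant assigned to one of the four designs.
- **Sites.** There are three recruiting locations. The plan does not say whether they share one list or have one each.

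**The concern.** When the block size equals the number of arms and is known, the designs already used in a block reveal those still to come. Open treatment supplies the past assignments. The participant code helps, because it carries both enrolment order and design. Withholding the list would not cure this, because the prediction needs only the history.

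The risk is selection bias between designs. The background section (Q1) reports that 46% of surveyed orthodontists chose the gingivally bevelled design for extrusion, and the section on scientific importance (Q4) says that experts favour different designs. Clinicians decide in practice whom to approach and when to report a recruit, and so which patient takes the next slot. Final inclusion depends on the ClinCheck report, which comes after consent. At the Richmond practice the design is relayed once consent is obtained. Read together, these steps leave room for an expected or known design to influence who is finally included. If easier teeth drift toward one design, the primary comparison is biased in a way that the analysis cannot be relied on to remove.

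**Working it through.** The plan states no figure for predictability, so there is none to reproduce.

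**Inputs.** From the protocol: 4 arms, blocks of 4, 80 teeth, 20 per arm, so 80/4 = 20 blocks. Assumptions: equal allocation within blocks, a patient with two study teeth (bilateral) takes consecutive slots, and the bilateral share *b*, which the documents do not give, runs from 0 to 100%.

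**1. Best guess, full history, one slot at a time.** The chance of a correct guess at slots 1 to 4 is 1/4, 1/3, 1/2 and 1. The mean is (1/4 + 1/3 + 1/2 + 1)/4 = 2.083/4 = 52.1%, against 25% with no information. For bilateral patients whose two slots are both still undrawn at enrolment, the figure by tooth is lower. If every patient were bilateral it would be (1/4 + 1/4 + 1/2 + 1/2)/4 = 37.5%.

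**2. What is certain before enrolment.** Slot 4 of a block is filled in one of two ways. Either a new patient starts there, and that design is known. Or a bilateral patient takes slots 3 and 4, and the two remaining designs are known as a pair but not by tooth. Exactly one patient per block is therefore affected, 20 per 80 teeth. With about 80/(1 + *b*) patients, the affected share is about (1 + *b*)/4. Simulation to exactly 80 teeth gives:

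| Bilateral share (assumed) | Patients affected | Teeth known exactly, of 80 | Pairs known, unordered |
|---|---|---|---|
| 0% | 25% | 20 | 0 |
| 25% | 31% | 16 | 4 |
| 50% | 37% | 13 | 7 |
| 75% | 44% | 11 | 9 |
| 100% | 50% | 0 | 20 |

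Among bilateral patients, the unordered pair is known in about 25% of cases (50% if all patients are bilateral).

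**3. An observer who sees one site only.** On one shared list with three equal sites, a site can be certain of slot 4 only if all four slots of the block fall there: 3 × (1/3)^4 = 1/27 = 3.7% of blocks. With site shares of 50/30/20% this is 7.2%, and with 80/10/10% it is 41%. If each site had its own list in blocks of 4, its own history would be the full history, and steps 1 and 2 would apply at each site.

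**4. Effect of changing the blocks.** Here the guesser picks the least-used design so far. By simulation, this is right for 52% of slots with fixed blocks of 4. It is right for 43% with hidden blocks of 8, 12 and 16 in random order, and for about 44% when those sizes are constrained to total 80. Without the constraint, at least one arm has fewer than 20 of the first 80 teeth in about 55% of runs. With it, every arm has exactly 20.

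**The case against.** A reader might infer that the last slot of every block is known in advance, and that a bilateral patient's two designs are often both known. The documents do not support either. The first holds only with one study tooth per patient and sight of the whole history. As the bilateral share rises from 10% to 100%, slot 4 is known exactly in 91% of blocks down to none. The second holds only for an unordered pair, and placing both designs in the same mouth blunts any steering between patients.

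Other objections carry weight:

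- The bilateral part depends on tooth-level randomisation, which Data Confidentiality and Storage, Q9 contradicts. The fixed-block point stands under either unit.
- That section also gives the list to the study team, which is the more direct failure of concealment. While it stands, block size hardly matters. But withholding the list alone would leave blocks of 4 predictable, so both need repair.
- The monthly meetings are described as progress updates, not as a sharing of assignments. With bilateral patients, enrolment order alone does not give the slot position. The headline figures therefore apply mainly to the person who relays assignments.
- Steering is limited. Study Procedures, Q4 has all non-excluded patients invited, inclusion rests on ClinCheck measurements, and predicted movement is recorded for each tooth, so some imbalance would be visible. This narrows the opening without closing it: the timing of a report, and features of a case that are not measured, remain open to choice.
- The survey of preferences concerns orthodontists in general and is not evidence about these investigators.

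**Conclusion.** The concern holds in a limited form. With one stated block size equal to the number of open arms, a person with the full ordered history guesses the next slot correctly 52% of the time instead of 25%. One patient per block enters with either the fourth-slot design or the remaining pair already known to that person. This is 25% to 50% of patients across the assumed bilateral range. The upper part of that range concerns unordered pairs, not designs known by tooth. For a clinician who sees only one of three equal sites on a shared list, certainty arises in about 4% of blocks.

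The result rests on equal allocation within blocks, consecutive slots for bilateral patients and one shared list. The documents show an opening for selection bias. They do not show that anyone has used it, and its effect on the comparison of designs cannot be sized from them. The plan should be changed, because the repair is cheap and the bias could not be reliably removed afterwards.

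**What to change.** 1. In Study Procedures, Q6 and Data Confidentiality and Storage, Q9, replace the fixed block size with computer-generated permuted blocks of randomly ordered, undisclosed sizes (for example 8, 12 and 16), constrained to total 80 so that each arm is still allocated exactly 20 teeth. Do not print the sizes in the protocol.
2. In Data Confidentiality and Storage, Q9, delete the provision of the list to the study team. Keep the list and block sizes with the biostatistician, who releases one assignment at a time. Without this, the first change has no effect.
3. Remove attachment type from the participant code.
4. Reconcile the tooth-level and participant-level statements of the randomised unit, and say whether the sites share one list.

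The cost is a few sentences, a new list from the same biostatistician and slightly more administration, with no extra patients. The gain has limits: best-guess accuracy falls to about 44%, not to 25%, and the very last slots can still be inferred because 20 per arm is public. What goes is the routine certainty at every fourth slot.

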The 2009 [name] et al study reported that maxillary lateral incisors were the teeth that most commonly required extrusion. This was a particularly inaccurate movement with aligners due to the difficulty of the aligners grasping the teeth and pulling them vertically. Boyd described absolute extrusion as being particularly challenging and advocated for the use of a mid-treatment correction such as elastics attached to a button bonded to the facial aspect, or combining extrusion with more predictable movements like lingual constriction or retroclination. Orthodontists have reported 70% to 80% of their aligner patients needing some level of mid-treatment intervention or refinement series to accomplish the goals of the treatment plan.

Though more recent studies have reported improvements in the predictability of most aligner movements, the measured outcomes still fall short of the anticipated changes. Because of the particular difficulties involved with controlling maxillary lateral incisor vertical positioning with aligners, there are many differing expert opinions on how lateral incisor extrusion should be accomplished. Glaser described in his 10 commandments of attachment design, that 4 mm wide gingivally beveled attachments on the maxillary lateral incisors would aid in more accurate extrusive movement. Gomez et al described the initial force systems generated by plastic aligners with and without attachments. They found that attachments created the force systems necessary to bodily tooth movement. Additionally, in a guest editorial in *The Angle Orthodontist* in 2008, Brezniak claimed that attachments added retentiveness and that extrusion was a difficult movement without attachments due to the clear aligners' tendency to concentrate force in the incisal portion of the teeth. No studies to date have specifically evaluated the challenging movement of maxillary lateral extrusion prospectively, comparing differences in attachment design and determining differences in their effectiveness.

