Clinicians can choose any attachment design whether it be the optimized attachments Invisalign provides, a horizontal attachment, or a beveled horizontal attachment, to name a few. A recent study found that orthodontists most frequently chose optimized (17%), rectangular (12%), incisally beveled rectangular (11%) or gingivally beveled rectangular attachments (46%) over other options for enhancing extrusion and that these choices were significantly different from those of general dentists (50%, 22%, 11%, and 3%, respectively). It is up to the clinician, using their expertise, to determine which attachment design best suits the goals of their treatment plan and there are no scientific data currently available. There are a limited number of prospective clinical studies in the literature on any aspects of orthodontic treatment using aligners.

2. * Describe the study hypothesis and/or research questions. Use lay language whenever possible.

Question: Which attachment design is most efficacious in extruding maxillary lateral incisor?

Null Hypothesis: There will be no difference in the efficacy among the four most-commonly used attachment designs (optimized, horizontal, gingivally-beveled horizontal, and incisally-beveled horizontal extrusion attachments) in extrusion of maxillary lateral incisor.

The goal of the study is to evaluate efficacy of different attachments and not their effectiveness on lateral incisor extrusion.

3. * Describe the study's specific aims or goals. Use lay language whenever possible.

The aim of this prospective, randomized controlled trial is to determine which of the four different attachment designs (optimized, horizontal, gingivally-beveled or incisally-beveled) offers more predictable extrusion of maxillary lateral incisors in patients treated with clear aligners (Invisalign, Align Technologies, Inc, USA). The secondary objective is to evaluate the accuracy of ClinCheck software in predicting the three-dimensional final position of the lateral incisor following extrusion using the attachment designs tested. The purpose is to be able to provide clinically-relevant recommendations for attachment planning for extrusion of maxillary lateral incisors during aligner treatment.

4. * Describe the scientific benefit or importance of the knowledge to be gained:

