This is a short term study that will last a maximum of 6 months. In the unlikely situation that the participant enters adulthood at any stage of the study (while actively on the first series of aligners or during data analysis), we will re-consent him/her using the adult consent document. Even though the study itself lasts only 6 months, the comprehensive orthodontic treatment would take much longer (12-18 months). In a vast majority of cases, incisor correction is done at the start and we expect all data analysis to be completed within a few months after the second scan. There are 2 possibilities when the issue of re-consenting arise:

- a. If the participants turns 18 while they are still on aligner therapy (irrespective of whether they are on initial series or beyond): In these cases, the study team will have an opportunity to see the participant in person for routine follow-up and will re-consent in person
- b. In the rare instance where the patients are off aligner therapy when data analysis is still in progress, the study team will reach out to the participant over phone and will seek re-consenting. We have checked the box for waiver of documentation of re-consent.

ID: HM20021396

View: SF_IRB_StudyLocation_NonVCUSitesDetails

Non-VCU Site Details

1. * Name of institution or site:

[name] Orthodontics, [name]

2. * Provide a description of the institution's or site's role in the research and what study activities they will be performing:

[name] owns and runs the exclusive orthodontic practice in Richmond. He is also an adjunct faculty in the Department of Orthodontics at VCU SoD.

[name] will identify potential participants and recruit them in the study if the patient meets the inclusion/ exclusion criteria and sign the informed consent. He will inform the PI once the consent is obtained. The PI will then relay the randomized assignment of the attachment design to [name]. The patient will be treated in [name] office and all necessary data (intraoral scans and ClinCheck) will be shared with the PI through a HIPAA-secure portal maintained by Align Technology. All patient information (including demographic information and photos) are maintained in the cloud and can be accessed only by a Invisalign-registered doctor or staff. This access is restricted by an username and password.

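### The assigned design reaches the orthodontist before any movement plan is saved, so prescribed extrusion can be set or changed with the arm known.

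*Combined protocol and SAP*

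**What the plan says.** **Order of events.** Study Procedures, question 4, obtains consent at the consultation from everyone not already excluded. The scan then goes to the manufacturer, and the ClinCheck report that decides final inclusion arrives a few days later. Data Confidentiality and Storage, question 9, says: "Once informed consent is obtained, the participants will be randomly assigned to one of the four attachment designs". Non-VCU Site Details, question 2, has the site tell the PI once consent is obtained, after which: "The PI will then relay the randomized assignment of the attachment design to" the site's orthodontist. Study Procedures, question 6, says a study team member "will then communicate the randomly assigned attachment design to the treating orthodontist based on the sequence generated by" the biostatistician, and continues: "The treating orthodontist will then put this information as an order to Align Technology for the fabrication of the attachment trays and clear aligners".

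**Preparation.** The team meets before the start to "calibrate on the screening criteria to determine eligibility as well as obtaining signatures and maintaining the consent documents". Planning of tooth movement and ordering of attachments are not on that list.

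**Limits on the prescription.** Study Population, question 4, sets a floor of 0.3 mm of ClinCheck extrusion. It sets no target or cap. The four arms are named by shape, without dimensions or position.

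**Outcome.** Study Procedures, question 6: "Comparison of initial and final positions (using Geomagic software) will be done to assess the efficacy of different types of attachments". The same answer has predicted and actual movement measured for each lateral incisor, but does not say how predicted movement enters the comparison of arms.

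**The concern.** The orthodontist must know the design to order it, so masking that person is not the issue. The issue is timing. As written, the amount of extrusion, the staging and the attachments on other teeth may still be open, or may be reopened, when the design is disclosed. Achieved movement depends on what was prescribed. If prescriptions drift apart by arm after assignment, a difference in initial-to-final movement is no longer attributable to the attachment alone.

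The trial says it studies efficacy rather than effectiveness (Background, Rationale and Goals, question 2). That aim calls for arms that differ in the attachment and in little else. A prescription altered after assignment is itself affected by the arm, so adjusting for it in the analysis does not cleanly restore the randomized comparison. Unrecorded differences in attachment size or position would raise the same difficulty.

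**Working it through.** **1. The plan's own figure.** Study Population, question 3: SD 1.25 (taken here as mm; no unit is printed), correlation 0.5, four levels, alpha 0.05. Effect size = V / [SD² × (1 − ρ)], λ = n × 4 × effect size, df = 3 and 3(n − 1).
- n = 15: 0.156 / (1.5625 × 0.5) = 0.1997; power 80.0%.
- n = 20: 0.114 / (1.5625 × 0.5) = 0.1459; power 80.0%.

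Both stated results reproduce. If one arm differs by s from the other three, V = 3s²/16, so V = 0.114 corresponds to s = √(0.114 × 16/3) = 0.78 mm.

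**2. Effect of extra prescription on one tooth.** Background, question 1, cites 29.6% accuracy for extrusion. Assume achieved = accuracy × prescribed. An extra 0.3 mm gives 0.296 × 0.3 = 0.089 mm, or 0.089 / 1.25 = 0.07 SD. If only 25% to 50% of teeth in one arm are affected (assumed), the arm mean moves by 0.25 × 0.089 = 0.022 mm to 0.50 × 0.089 = 0.044 mm.

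**3. Against sampling error.** The standard error of a two-arm difference with 20 independent teeth per arm is 1.25 × √(2/20) = 0.40 mm. With correlation 0.5 it is 1.25 × √(2 × 0.5/20) = 0.28 mm.

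**4. When it would matter.** Suppose every tooth in one arm is prescribed d mm more than in the other three, and there is no true attachment effect. Rejection rate of the nominal 5% test, 20 teeth per arm: independent groups use λ = 80V/SD², df 3 and 76; the plan's repeated measures model uses λ = 80V/[SD² × 0.5], df 3 and 57.

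| Accuracy | d (mm) | Shift (mm) | V | Independent | Repeated measures |
|---|---|---|---|---|---|
| 29.6% | 0.3 | 0.09 | 0.0015 | 5.4% | 5.8% |
| 29.6% | 0.5 | 0.15 | 0.0041 | 6.2% | 7.4% |
| 29.6% | 1.0 | 0.30 | 0.0164 | 10.1% | 15.8% |
| 80% (assumed) | 0.3 | 0.24 | 0.0108 | 8.3% | 11.8% |
| 80% (assumed) | 0.5 | 0.40 | 0.0300 | 15.0% | 26.4% |
| 80% (assumed) | 1.0 | 0.80 | 0.1200 | 50.6% | 82.2% |

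Both models are shown because the calculation is for repeated measures while teeth are randomized individually. The values of d and the 80% accuracy are illustrations. The background says more recent studies report better predictability but gives no newer figure for extrusion.

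**The case against.** The strongest reply is that the plausible bias is negligible. A shift of 0.02 to 0.04 mm is less than half of the 0.1 mm increment in which extrusion is analysed. That stands for small prescription differences; it does not cover large ones, which the plan neither prevents nor records.

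Second, predicted movement is already measured. If achieved movement is proportional to prescription, the ratio of actual to predicted does not move: 0.089/0.3 = 0.178/0.6, about 29.6% either way. This is a real partial safeguard. But the documents do not name a ratio as the between-arm measure, and the denominator could be set after assignment.

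Third, question 6 calls only for the assigned design to be put into the order, and an eligibility ClinCheck already quantifies extrusion. No passage describes re-planning after assignment. That also stands: the point is what the sequence permits.

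A reader might infer more from the background: that experts link success to attachment width, or that the trial's orthodontists favour one design and would compensate in the others. The text does not support this. "4 mm wide gingivally beveled attachments on the maxillary lateral incisors would aid in more accurate extrusive movement" is one expert's advice. "gingivally beveled rectangular attachments (46%) over other options for enhancing extrusion" comes from a survey of orthodontists in general; it is not data on this trial's operators, and 46% is a minority. Neither shows anyone changing prescribed movement to suit an attachment.

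**Conclusion.** The concern holds in a limited form. The documents let the movement plan be set or revised after the arm is known, and no saved pre-assignment plan exists against which a change could be seen. The resulting bias cannot be sized from the documents. On the cited accuracy and a 0.3 mm difference it is about 0.09 mm per affected tooth, small against an SD of 1.25 mm and a standard error near 0.40 mm. It becomes material with prescription gaps nearer 1 mm, or with much higher accuracy. These figures assume proportional response, a shift confined to one arm, and an SD in mm. They do not include any effect of attachment size, for which the documents give no basis.

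A reader might infer that the comparison is likely to be spoiled, or point out that 0.02 to 0.04 mm is 25% to 50% of the 0.09 mm expected on a tooth at the 0.3 mm floor. That ratio uses the smallest eligible tooth and an assumed frequency, so it is not evidence of a serious distortion. The change is worth making because it costs almost nothing and cannot be made once orders have been placed.

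**What to change.** Amend Study Procedures, question 6, Data Confidentiality and Storage, question 9, and Non-VCU Site Details, question 2, so that they give one sequence:

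1. Release the design only after ClinCheck eligibility is confirmed and the movement plan (prescribed lateral incisor extrusion, staging, other maxillary attachments) has been saved with a date.
2. Log any later change with its reason, and tabulate changes by arm. Changes remain possible; they become visible.
3. Use the saved pre-assignment prescribed extrusion as the baseline value in the between-arm comparison.
4. Keep the plan actually manufactured as the predicted model for the ClinCheck-accuracy objective. Scoring teeth against a plan that was not manufactured would damage that objective.
5. Record the size and position of each attachment as ordered, so that the arms can be checked for differences other than shape. The choice of dimensions stays with the investigators.

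Item 3 does not remove a change made after assignment. Items 1 and 2 limit such changes and show how many occurred. The cost is a short delay in releasing the assignment and a small log.
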